3.3 Exploratory analyses

Exploratory analyses guided by the findings will be performed.

4. Population

A power calculation was performed, based on a change of 0.21 BMI_z at 12 months with a standard deviation of 0.24 in the standard care group, and with a non-inferiority limit of 0.12 BMI_z between the groups. To reach 80 % power with a significant level of 0.05, a study population of 100 participants, 50 in each group was needed.

5. Missing data

In the case of missing data, the last observation carried forward approach will be used when data is available from 6- or 9-month follow up. Values that are outside the time-range for the visits will be included in the analysis when needed.

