3.1 Primary outcome

The primary outcome of this clinical trial is the change in BMI_z from baseline to 12 months. The hypothesis of the study is that the change in BMI_z in the intervention group is non-inferior to the control group. This will be analysed using a non-inferiority approach.

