3.2 Secondary outcomes

The effect of semi-digital care on change in BMI_z, weight, metabolic markers and dietary habits after one year (for BMI_z and weight also at 3, 6 and 9 months) will be investigated.

Analyses: For continuous variables regarding change in BMI_z, weight and blood markers the means between the groups will be compared. A non-parametric test to compare frequencies for categorical variables will be used. We will also use logistic regression models to evaluate the odds for change in zBMI larger than 0.25 sd.

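### Filling a missing 12-month BMI_z with the 6- or 9-month value can bias the non-inferiority comparison, by an amount the SAP gives no basis to bound

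*SAP*

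**What the plan says.** SAP section 3.1 fixes the endpoint: "The primary outcome of this clinical trial is the change in BMI_z from baseline to 12 months", analysed for non-inferiority. Section 4 describes the sample-size calculation as "based on a change of 0.21 BMI_z at 12 months with a standard deviation of 0.24 in the standard care group". The margin enters it "with a non-inferiority limit of 0.12 BMI_z between the groups", and the result is "a study population of 100 participants, 50 in each group was needed".

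Section 5 covers gaps in follow-up: "the last observation carried forward approach will be used when data is available from 6- or 9-month follow up". It adds that measurements taken outside the visit window may be used when needed. No other way of handling a missing 12-month value is named, and no sensitivity analysis.

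Section 3.2 shows that the intermediate visits are analysed in any case: "for BMI_z and weight also at 3, 6 and 9 months".

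**The concern.** A 6- or 9-month change is not the 12-month change. Entering it as if it were assumes that nothing happens to BMI_z after the last visit. In a superiority trial, diluting a widening gap is usually conservative. In a non-inferiority trial, the same dilution moves the estimate towards the claim.

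A second route to bias is an unequal carried share. If both arms are still improving, the arm with more carried values looks worse than it is.

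The trial's conclusion rests on one confidence limit set against 0.12. The error rate and power in section 4 ("To reach 80 % power with a significant level of 0.05") are therefore what is at stake. The point concerns children who have a 6- or 9-month value but no 12-month value.

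**Working it through.** **Inputs from the SAP (section 4).** 50 per arm, SD 0.24, standard-care change 0.21, margin 0.12, alpha 0.05, power 80%.

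**Assumptions, because the SAP is silent.** Carried share m; share f of the 12-month gap already present at the carried visit; sidedness of alpha.

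**1. The SAP's own figure.** n per arm = 2 × (1.645 + 0.842)² × 0.24² / 0.12² = 49.5, which rounds up to 50. The stated 100 is reproduced with one-sided 0.05 and a true difference of zero. One-sided 0.025 would need 63 per arm, so one-sided 5% is used below. SE = 0.24 × √(2/50) = 0.048.

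**2. Equal carried share, true difference 0.12.** The expected estimate is 0.12 × [1 − m(1 − f)]. The false non-inferiority rate is approximately Φ(−1.645 + m(1 − f) × 0.12/0.048).

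| Situation at the carried visit | m = 10% | m = 20% | m = 30% |
|---|---|---|---|
| Linear divergence, month 9 carried (f = 0.75) | 5.7% | 6.4% | 7.3% |
| Linear divergence, month 6 carried (f = 0.5) | 6.4% | 8.2% | 10.2% |
| No gap yet (f = 0) | 8.2% | 12.6% | 18.5% |
| Gap complete (f = 1) | 5.0% | 5.0% | 5.0% |
| Gap 25% larger than at 12 months (f = 1.25) | 4.4% | 3.8% | 3.3% |

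Example: m = 20%, f = 0.5 gives an estimate of 0.108 and Φ(−1.645 + 0.012/0.048) = Φ(−1.395) = 8.2%. Simulation with 20,000 trials per scenario agrees (8.1% for this cell, 4.9% with no missing data).

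**3. Does the narrower interval matter?** Assume variance grows in proportion to time and standard care declines steadily. At 30% carried from month 6, the linear case moves from 10.2% to about 11%. For f = 0, the variance per child is
- standard care: 0.0576 × 0.85 + 0.3 × 0.7 × 0.105² = 0.0513;
- semi-digital: 0.0576 × 0.85 + 0.3 × 0.7 × 0.015² = 0.0490.

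The SE is √(0.1003/50) = 0.0448, and Φ(−1.645 + 0.036/0.0448) is about 20%. With the gap complete by the carried visit, the rate stays at about 5%. The error is mainly bias.

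**4. Unequal carried share.**
- *Truly equal arms*, steady decline, 30% (semi-digital) versus 10% (standard care) carried from month 6. The change at month 6 is 0.105, so the spurious difference is (0.30 − 0.10) × 0.105 = 0.021 against semi-digital care. The variances per child are 0.0513 and 0.0557, so the SE is √(0.1070/50) = 0.0463. Power = Φ((0.12 − 0.021)/0.0463 − 1.645), about 69%.
- *True difference 0.12*, linear change, month 6 carried. With 20% carried in standard care and 10% in semi-digital care, the false-claim rate is about 10%. With the shares reversed it is about 5%.

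**5. What a repeated-measures analysis costs.** Take 30% missing at month 12 in each arm, every child with a month-6 value, and the same growing variance. The variance of an arm's 12-month mean is (0.0576/50) × k.

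| Last visit of the missing 30% | k | SE | Power |
|---|---|---|---|
| All month 9 | 0.75 + 0.25/0.7 = 1.107 | 0.0505 | 77% |
| Half month 6, half month 9 | 0.5 + 0.25/0.85 + 0.25/0.7 = 1.151 | 0.0515 | 75% |
| All month 6 | 0.5 + 0.5/0.7 = 1.214 | 0.0529 | 73% |

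Under carrying forward the SE is 0.0453 (all month 6) to 0.0464 (all month 9), an apparent power of 84% or 83%. With 10% missing, the repeated-measures power is 78-79%.

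**The case against.** The strongest reply is that nothing in the SAP shows that the arms separate late or that many 12-month values are missing. That stands. A reader might infer that the rule always favours a non-inferiority claim, or that the false-claim rate will be some 7-20%. The documents support neither. The direction depends on the trajectory: there is no inflation if the gap is complete by the carried visit, and the rule is conservative if the gap later narrows. The 20% figure is a corner case, and 10% carried under linear divergence gives only about 6%.

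Other points on that side:
- Section 5 admits out-of-window measurements, so a late 12-month visit need not trigger carrying forward. This may lower the carried share, but the SAP does not say by how much.
- The Skåne site was excluded (SAP section 2), so the analysed number may be below 50 per arm. A larger SE slightly reduces the inflation: with 35 per arm, an assumed figure, the 8.2% cell becomes 7.6%.
- If alpha is one-sided 0.025, the baseline is 2.5% and the rates are lower (4.4% in that cell), but the inflation remains.
- A repeated-measures model is unbiased only if missingness depends on observed values. It is biased too if children drop out because of an unseen 12-month result.

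These points limit the size of the concern. None shows that carrying forward estimates the 12-month difference.

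**Conclusion.** The concern holds in conditional form. Section 5 makes the primary non-inferiority test depend on an assumption that BMI_z is static after month 6 or 9, and nothing in the SAP supports or tests that assumption. False non-inferiority is about 6-11% instead of 5% for 10-30% carried under linear divergence, and about 20% only in the extreme case. In the unequal-share example, power falls from 80% to about 69%.

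These figures rest on 50 per arm, SD 0.24, one-sided 5%, and assumed carried shares and trajectories; the upper ends and the power figures also assume variance proportional to time. Severity: should be fixed, rising to must be fixed if the carried share proves large.

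**What to change.** In section 5, replace carrying forward for BMI_z with text such as: change in BMI_z at 3, 6, 9 and 12 months is analysed in one mixed model for repeated measures with arm, visit, arm by visit and unstructured covariance; no value is carried forward; non-inferiority is judged on the 12-month arm difference and its confidence limit against 0.12. The same model supplies the 3-, 6- and 9-month comparisons of section 3.2.

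Keep carrying forward as a sensitivity analysis. Beside it, worsen the missing 12-month values in the semi-digital arm step by step until the conclusion changes, and report that point. Stopping at 0.12 would be too mild: with 30% missing it moves the estimate by only 0.3 × 0.12 = 0.036. Report the number of missing 12-month values by arm and by last visit.

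The work is SAP wording and a few lines of code on visits already planned. The real cost is precision. With 30% missing and variance growing with time, the standard error is about 0.051-0.053, and power is roughly 6 to 11 points below what carrying forward appears to give. It also falls below the planned 80%. The loss is smaller with less missing data.
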